## 15.3 Modified Enrolment Criteria for Retrospective Arm

### 15.3.1 Retrospective Inclusion Criteria

Patients enroled in this study must meet the following criteria:

1. Male gender
2. Diagnosis of symptomatic BPH
3. Age  $\geq$  50 years
4. Presented with acute urinary retention with at least one failed trial without catheter prior to invasive surgery (index procedure)
5. Underwent invasive BPH surgery (TURP, HoLEP, etc.) while in retention and performed by site between June 01, 2015 and December 31, 2015.
6. Prostate volume  $\leq$  100 cc as measured by ultrasound, specimen (tissue) weight, or other standard method for prostate evaluation

### 15.3.2 Retrospective Exclusion Criteria

Patients will be excluded from the study if any of the following conditions apply.

1. Underwent known BPH surgery prior to the AR and index procedure
2. History of neurogenic or atonic bladder
3. Acute renal failure
4. History of prostate or bladder cancer prior to index procedure
5. Known coagulopathies or subject on anticoagulants within 3 days of index procedure (excluding up to 100mg ASA)
6. Known bladder stones within 3 months of index procedure

7. Known prostatitis requiring treatment (antibiotics) within year prior to index procedure
8. Unable or unwilling to provide informed consent

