### 8.2 Exclusion Criteria

---

Subjects will be excluded from the study if any of the following conditions apply.

1. An obstructive or protruding median lobe of the prostate
2. Previous BPH surgical procedure
3. Previous pelvic surgery (i.e. incontinence sling, trauma repair, penile implants, artificial sphincter) or irradiation
4. Urethral conditions that prevents insertion and delivery of device system into bladder (i.e. urethral strictures, meatal stenosis, bladder neck contracture)

5. Chronic retention volume of >1500 mL
6. Has not had prostate cancer excluded
7. History of prostate or bladder cancer
8. Biopsy of the prostate within the 6 weeks prior to Index Procedure
9. History of neurogenic or atonic bladder
10. Acute or chronic renal failure
11. Known coagulopathies or subject on anticoagulants within 3 days of index procedure (excluding up to 100mg ASA)
12. Known bladder stones within the prior 3 months or treatment within 12 months
13. Prostatitis requiring treatment (antibiotics) within the last year
14. Other co-morbidities that could impact the study results such as:
  - severe cardiac arrhythmias uncontrolled by medications or pacemaker
  - congestive heart failure NYHA III or IV
  - history of uncontrolled diabetes mellitus
  - significant respiratory disease in which hospitalisation may be required
  - known immunosuppression (i.e. AIDS, post-transplant, undergoing chemotherapy)
15. Life expectancy estimated to be less than 5 years
16. Desire to maintain fertility post procedure
17. Unable or unwilling to complete all required questionnaires and follow up assessments (e.g. lives out of area)
18. Unable or unwilling to sign informed consent form
19. Currently enroled in any other clinical research trial that has not completed the primary endpoint

Refer to Section 15.3 for the modified enrolment criteria for the retrospective arm.

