**Table 12 Retrospective Chart Review Design Quality Checklist**

Issue and Suggested Solution		Study Design
Chart Review Inappropriate for Study Question		

 
Establish whether necessary information is available in the chart.
 
Define outcome variables to be collected a priori.
 
Establish if there are sufficient charts to perform the analysis with adequate precision.
 
		
 
Participating sites are research centres, two sites have presented their own UroLift datasets at medical conferences.
 
The EDC system (host of the eCRFs) and source worksheets will guide the abstractor on exact data collection requirements.
 
Participating PIs were qualified due to their high number of BPH patients they treat.
 

Investigator Conflict of Interest or Bias		

 
Declare any conflict of interest.
 
Provide evidence of Ethics Committee approval.
 
Submit the data collection form, as well as the coding rules and definitions.
 
		
 
Financial Disclosure and conflict of interest forms will be completed by all Principal Investigators.
 
A regulatory binder will be maintained for HRA and EC correspondence including approval materials.
 
Study will utilise EDC with eCRF completion instructions. MedDRA coding will be used and embedded in the EDC.
 

Patient Sample is Non-Representative		

 
Case selection or exclusion using explicit protocols and well described the criteria.
 
Ensure all available charts have an equal chance of selection.
 
		
 
Study design requires that all surgeries during a set amount of time are evaluated for inclusion, and criteria are well matched to the prospective investigation.
 
The NHS trust system is consistent across centres.
 

Chart Abstraction is Not Systematic (Misclassification Bias)		

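### The retrospective criteria omit several prospective exclusions, so surgical men who would have been ineligible for PUL can enter the unadjusted between-arm comparisons, hospital stay above all

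*Combined protocol and SAP*

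**What the plan says.** Section 8.2 lists 19 exclusions for PUL men. Item 14 is introduced as "Other co-morbidities that could impact the study results such as" and names uncontrolled arrhythmia, NYHA class III or IV heart failure, uncontrolled diabetes, immunosuppression and "significant respiratory disease in which hospitalisation may be required". Other items exclude life expectancy under 5 years (15), "Acute or chronic renal failure" (10), previous pelvic surgery or irradiation (3), bladder-stone treatment within 12 months (12) and "An obstructive or protruding median lobe of the prostate" (1). Under section 10.2.2, a PUL man enrolled against any criterion is a significant violation whose data may be dropped.

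Section 15.3.2, under "Patients will be excluded from the study if any of the following conditions apply", has eight items. Its only renal item is "Acute renal failure".

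Section 6.1 calls the surgical population matched, section 13.9 relies on a matched dataset in the risk-to-benefit rationale, and Table 12 says that the "criteria are well matched to the prospective investigation". Section 16.6 (Retrospective Arm) compares the arms by t-test or a non-parametric alternative, and by chi-square or Fisher's exact test. The outcomes include hospitalisation time, related AEs and SAEs, retention recurrence and retreatment. Co-morbidities are abstracted under section 15.8.1, but no planned between-arm analysis adjusts for them or is restricted by them.

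**The concern.** The protocol itself identifies the item 14 conditions as able to affect the results, and one of them is defined by the prospect of admission. A man with such a condition is kept out of one arm and is a valid comparator in the other. If these conditions lengthen stay or raise event rates, the arms will differ with no difference between the treatments, and nothing in section 16.6 separates the two explanations. The comparison is a stated objective in section 6.1, and its results are meant to inform a larger controlled study. Readers told that the arms are matched would have little reason to suspect a case-mix difference written into the criteria.

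**Working it through.** **Step 1: the two lists side by side.**

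| Condition | Prospective (8.2) | Retrospective (15.3.1, 15.3.2) |
|---|---|---|
| Serious comorbidity | Excluded (14) | No counterpart |
| Life expectancy under 5 years | Excluded (15) | No counterpart |
| Renal failure | Acute and chronic excluded (10) | Acute only (3) |
| Pelvic surgery or irradiation | Excluded (3) | No counterpart |
| Bladder stones | Known within 3 months, or treated within 12 (12) | Known within 3 months only (6) |
| Obstructive median lobe | Excluded (1) | No counterpart |
| Retention volume over 1500 mL | Excluded (5) | Not in the exclusions; largely covered by the Table 2 definition of acute retention |

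The retrospective inclusion list restores none of the first six. Section 15.3 is headed as modified criteria, so some difference is intended, but no reason is given for these omissions.

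**Step 2: does the analysis repair it?** Section 16.6 plans no matching, restriction, weighting, stratification or regression. The comorbidity data that would allow it are collected, though only under a general entry.

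**Step 3: how large could it be?** The documents give no event rate, SD or retrospective sample size for this comparison, so there is no plan figure to reproduce. Everything below is assumed except that 55 is the PUL maximum (section 7). Assume 55 men per arm, no true treatment difference, and a share f of surgical men who would have failed the prospective exclusions.

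*SAEs.* Assume a rate p = 5% in men who meet the prospective criteria and a relative risk RR in those who do not. The surgical rate is q = p(1 − f) + p × RR × f. For f = 20% and RR = 3: 0.05 × 0.8 + 0.05 × 3 × 0.2 = 7.0%. The last column is the exact probability that Fisher's test rejects at 5%.

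| f | RR | Surgical rate | Apparent ratio | Fisher rejects |
|---|---|---|---|---|
| 0 | – | 5.0% | 1.0 | 0.9% |
| 10% | 2 | 5.5% | 1.1 | 1.0% |
| 20% | 3 | 7.0% | 1.4 | 2.0% |
| 30% | 3 | 8.0% | 1.6 | 3.3% |
| 40% | 4 | 11.0% | 2.2 | 10.6% |

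In 55 men the excess is 55 × 0.005 = 0.3 events at the low end and 55 × 0.06 = 3.3 at the high end. For SAEs the effect is mostly a shifted point estimate rather than a false significant result.

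*Hospital stay.* Assume SD 2 days and d extra days in the otherwise ineligible men. The spurious difference is f × d. The surgical variance is 4 + f(1 − f)d², and the standard error is √[(4 + surgical variance)/55]. For f = 20% and d = 2: difference 0.4 days, surgical variance 4.64, standard error √(8.64/55) = 0.396, z = 1.01, and a two-sided 5% test rejects with probability 17.2% (normal approximation).

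| f | d (days) | Spurious difference (days) | False-positive rate (nominal 5%) |
|---|---|---|---|
| 10% | 1 | 0.1 | 5.8% |
| 20% | 2 | 0.4 | 17.2% |
| 30% | 2 | 0.6 | 32.2% |
| 40% | 3 | 1.2 | 79.7% |

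Hospital stay is the more exposed outcome: it is continuous, and it carries no relatedness filter.

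**The case against.** A reader might infer that sicker surgical men did enter and that PUL is therefore made to look safer and more effective. The documents do not support that, for four reasons.

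- The criteria permit such men; nothing shows how many there are.
- There is selection the other way. Surgical men had already been accepted for an invasive operation, and under section 15.5 a man who cannot be reached or declines consent contributes no data, which removes men who have since died. Surgical events also come from charts, where available and in restricted categories (15.8.2, 15.8.3), while PUL men are asked about all adverse events at each visit (14.5). Under-recording would favour surgery.
- The SAE comparison is naturally read as one of related events, and many admissions for heart, lung or metabolic disease would be judged unrelated. This dampens the effect on SAEs but does not touch hospital stay.
- Not every omission marks a sicker man. The median lobe is a matter of anatomical comparability. Exclusion 5, "Chronic retention volume of >1500 mL", is a minor point, because Table 2 defines acute retention as a residual below 1500 mL and retrospective inclusion 4 requires acute retention. The case-mix argument rests mainly on item 14, life expectancy and chronic renal failure.

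It is also fair to say that the primary and safety assessments do not use the retrospective arm, that section 16.6 says the comparison is not powered, and that section 16.7 sets no success criterion. These points limit the consequence. They do not remove the bias: statistical significance is still to be assessed, and lack of power is no protection against arms that differ by design. The opposing selections are further uncontrolled differences and cannot be counted on to cancel this one.

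**Conclusion.** The point holds in a limited form. The retrospective criteria allow men who would have been ineligible for PUL into unadjusted tests, which contradicts the description of the arms as matched and the criteria as well matched. Hospitalisation time is the main exposure; related SAEs, retention and retreatment are affected less. The likely direction favours PUL but is not certain. The figures of 0.1 to 1.2 days and 5.5% to 11.0% rest wholly on assumed shares, risks, SD and sample size; they show what the criteria could produce and do not estimate what happened. The primary TWOC result and the single-arm safety rate are unaffected. The change is worth making because it is cheap and removes part of a known case-mix difference.

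**What to change.** 1. Apply to the retrospective arm every prospective exclusion that the chart can verify: the item 14 conditions, chronic renal failure, prior pelvic surgery or irradiation, stone treatment within 12 months, documented obstructive median lobe and, where a chart allows it, limited life expectancy.
2. If abstraction has begun, pre-specify the section 16.6 comparisons in the surgical men who would have met these exclusions, and show the full surgical group alongside.
3. In section 15.8.1, name the item 14 conditions, chronic renal failure and median lobe as fields to record where charted, and state how unrecorded items are treated. One option is to count them as absent in the main restricted comparison and repeat it without the men whose status cannot be determined.
4. Tabulate comorbidity by arm with the baseline demographics.
5. Replace the wording on matching in sections 6.1 and 13.9 and in Table 12 with a statement of which criteria differ and why.

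The cost is protocol wording and a few abstraction fields, since co-morbidities are already collected in general form. The downside is a smaller surgical comparison group. Some items, such as NYHA class, degree of control of arrhythmia or diabetes, and life expectancy, may not be determinable from charts, so the restriction will be incomplete and should be reported as such.

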## 15.2 Subject Identification

Case abstractors will create a Master List of all invasive BPH surgeries (TURP, HoLEP, etc.) performed by the site from June 1, 2015 to December 31, 2015. Each case will be reviewed against the study selection criteria (See Section 15.3) and case abstractors will document enrolment status for each subject and the reason(s) for that decision. Patients meeting criteria will be contacted for consent.

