#### 15.4 Enrolment Procedures- Retrospective arm

---

A retrospective patient is considered enroled in the clinical study if his records meet inclusion and exclusion criteria and has provided proper consent. Once subject is enroled, data will be extracted from the medical chart and entered into the study EDC.

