#### 15.5 Patient Informed Consent – Retrospective arm

---

A consent form specific to the retrospective arm will be utilised to inform patient of the study, the chart review process and that Sponsor representatives and government bodies may access personal information. If consent is denied, or the patient is no longer reachable, the enrolment log will record reason, and no further data will be collected or retained. At least three attempts, using multiple methods, should be used to contact potentially eligible patients, at the discretion of the PI.

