### **Retrospective Arm**

The following baseline and procedural data points will be summarised for both the retrospective and the prospective arms. Although the study is not powered to make comparisons between the retrospective surgical patients and the prospective Urolift subjects, comparisons in the observed data will be made statistically. Continuous variables will be compared using a t-test or non-parametric alternative, binary data points will be compared using chi-square or Fisher's exact test.

- 1) Baseline demographics

- 2) Duration of catheterisation to procedure (days)
- 3) Procedure time
- 4) Hospitalisation time

The following outcomes post procedure will be summarised for the retrospective surgical group and will compared to the results obtained in the prospective study. The statistical significance of any observed differences will be assessed.

- 1) Total numbers of related AE, SAE, and Clavien-Dindo  $\geq$ IIb individually
- 2) Percent procedure/device related AE rates by month post index procedure and by severity
- 3) Retreatment post index intervention by time to event and by month
- 4) Medical treatment post index intervention by time to event and by month
- 5) Urinary retention recurrence rates at 1 month, 6 weeks and at 3, 6 and 12 months
- 6) Post-procedure TWOC success percent
- 7) Catheterisation use

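### Surgical men must consent after their 12-month outcome window has closed, so fatal surgical events cannot be observed and the between-arm SAE and Clavien-Dindo comparison is not like-for-like on deaths

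*Combined protocol and SAP*

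**What the plan says.** Section 15.3.1 admits men whose invasive BPH surgery was "performed by site between June 01, 2015 and December 31, 2015". The opening of Section 15 and Section 15.8.3 set the outcome window at 12 months after that surgery.

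Entry depends on consent sought later. Section 15.2 has sites list all invasive BPH surgeries in the window and document a decision and reason for each; then "Patients meeting criteria will be contacted for consent". Exclusion 8 in 15.3.2 is "Unable or unwilling to provide informed consent". Section 15.4 counts a man as enrolled only when his records qualify and he "has provided proper consent. Once subject is enroled, data will be extracted from the medical chart and entered into the study EDC". Under 15.5, if consent is refused "or the patient is no longer reachable, the enrolment log will record reason, and no further data will be collected or retained". Nothing in Section 15 provides a waiver, consent by a relative, or any other route for men who have died.

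The bias checklist (Table 12) answers the risk of a non-representative sample with "Study design requires that all surgeries during a set amount of time are evaluated for inclusion". It does not mention survival to the time of consent.

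Section 16.6 (Retrospective Arm) then compares the arms on "Total numbers of related AE, SAE, and Clavien-Dindo" grades, among other outcomes, and assesses statistical significance. Death is SAE criterion (a) in Section 14.1 and grade V in Table 10.

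**The concern.** PUL men consent before treatment (Sections 10.2.1 and 10.3). Their deaths must be reported even if unrelated (Section 17.5), and they stay in the safety population until any alternative surgery (Section 16.3). Surgical men consent only after the event. A man who died in the meantime cannot consent, so survival becomes a condition of entry in one arm only, and it is itself an outcome under comparison.

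Comparing the benefits and risks of PUL with surgery is a stated objective (Section 6.1) and part of the risk-to-benefit rationale (Section 13.9). The results are also meant to inform a larger randomised trial. A test in which only one arm can record a fatal event could mislead that planning. Adjustment on chart variables cannot repair it, because no records of the men who died are held.

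**Working it through.** The plan gives no sample size calculation, mortality figure or retrospective sample size, so there is no stated figure to reproduce. The check is date arithmetic.

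**Inputs**
- Last index surgery: 31 December 2015 (15.3.1).
- Outcome window: 12 months (Section 15, 15.8.3). The last window closes 31 December 2016, 366 days later.
- Earliest protocol date: Revision A, 30 May 2017 (revision history).
- Revision B, which added exclusion 8: 31 January 2018 (revision history).
- Planned first patient in: 15 April 2018 (Section 1).

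**Shortest gap from surgery to consent** = possible consent date − 31 December 2015
- Revision A: 366 + 150 = 516 days (17.0 months), 150 days after the last window closed.
- Revision B: 366 + 365 + 31 = 762 days (25.0 months), 396 days after.
- First patient in: 366 + 365 + 105 = 836 days (27.5 months), 470 days after.

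These are minimum gaps, and all exceed 366 days. For surgery on 1 June 2015 they are 729, 975 and 1,049 days. Every man able to consent has outlived his whole window, so observable 12-month surgical deaths are zero on any date the documents allow.

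**Possible size (assumptions only).** Suppose n eligible surgical men and all-cause 12-month mortality p. Expected deaths are n × p, and the chance of at least one is 1 − (1 − p)^n. The documents give neither n nor p.
- n = 30: p from 0.5% to 5% gives 0.15 to 1.5 expected deaths; chance of at least one 14% to 79%.
- n = 55: 0.28 to 2.75 expected deaths; chance 24% to 94%.
- n = 100: 0.5 to 5 expected deaths; chance 39% to 99%.

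Under the consent rule the chance is 0% in every row. These are ceilings, because they count deaths from any cause. The safety assessment in Section 6.3 concerns SAEs related to BPH intervention through 3 months, and the first post-procedure item in 16.6 opens with related events. Deaths missing from a related-event count are a subset of these, possibly none.

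**Selection in the other arm.** Section 8.2 excludes PUL candidates with acute or chronic renal failure (item 10), serious co-morbidity (item 14) or life expectancy under 5 years (item 15). Section 15.3.2 has only acute renal failure in common with these. The PUL arm is thus screened for frailty at entry, and the surgical arm is filtered afterwards by survival, contact and consent.

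**The case against.** The strongest reply concerns consequence. The study is a feasibility study with no formal success criterion (Section 16.7), its primary assessment is single-arm TWOC success (Section 6.2), and 16.6 says that the comparison is not powered. Section 15.7 admits that retrospective series carry many sources of bias. Losing fatal events in the surgical arm works against the sponsor's device on that component, so it cannot by itself manufacture an advantage for PUL on SAEs. All of this stands, and it limits the priority of the point. It does not make a test that one arm cannot fail on deaths informative.

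A reader might go further and infer that surgery will look safer overall because its frailest men are removed. The documents do not support that. PUL men are also selected for better health, by entry criteria that the surgical arm lacks, and the two selections may partly offset each other. For retreatment and retention recurrence, no direction can be argued from the text.

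A reader might also put a figure on the loss: assuming 2% to 8% mortality in 50 men gives 50 × 0.02 = 1 to 50 × 0.08 = 4 deaths. Both inputs are outside the documents, and the result is all-cause, whereas the safety assessment and the 16.6 item concern related events.

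Nor is the Table 12 entry false. All surgeries are indeed evaluated. The entry is incomplete, because evaluation does not lead to inclusion for men who have died or cannot be reached.

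**Conclusion.** The point holds for fatal events. Deaths within 12 months of surgery are unobservable in the surgical arm by design, while PUL deaths are counted. The SAE and Clavien-Dindo comparison in 16.6 is therefore not like-for-like on deaths. This rests only on the protocol's own dates and consent rules, and it holds at the earliest date they allow (516 days against a 366-day window).

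The number of related deaths lost cannot be derived from the documents. The ranges shown are all-cause illustrations under assumed mortality and arm size. The net bias in non-fatal outcomes, retreatment and retention recurrence is of unknown direction. The primary assessment is untouched. The comparison should be corrected, but the defect does not invalidate the study.

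**What to change.** - **Section 16.6.** Make the between-arm SAE and Clavien-Dindo comparison on non-fatal events. List fatal events (grade V) descriptively, with a note that they are unobservable in the surgical arm. Label all surgical-arm outcomes as *in men alive, reached and consenting at study time*. The label is still needed for non-fatal events, because any suffered by men who later died before contact are also missing.
- **Participant flow.** Report the path from Master List to enrolment by reason (died, unreachable, declined), using the records that 15.2 and 15.5 already require.
- **Section 15.5, if ethics agreement is obtained.** The rule that "the enrolment log will record reason, and no further data will be collected or retained" conflicts with coding time of death for men who have not consented. Amend it so that the log can give one aggregate count, without identifiers, of deaths within 12 months of surgery, shown beside the descriptive line.
- **Table 12.** Add survival and consent to the representativeness entry.

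The cost is wording in 16.6 and Table 12, reason categories in an existing log, a vital-status check at each site, and possibly an ethics submission. The main statistical price is that any PUL death moves from the test to a descriptive line. The difference in co-morbidity screening between the arms remains and should be stated as a limitation.
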